Baseline DENV and ZIKV serostatus will be determined via IgM antibody and IgG ELISA assays, with subject results reported as either 'positive' or 'negative'. If a subject has a positive ZIKV result from either the IgM or IgG ELISA assays, they will be considered ZIKV seropositive at baseline. If a subject has inconclusive results for their baseline flavivirus immune status, they will not be included in analyses stratified by baseline flavivirus immune status but will be included in analyses of all subjects.

Post-Baseline Seropositivity

Seropositivity post-baseline is defined as a titer ≥ 10 and ≥ 100 for ZIKV MN50 and a titer ≥ 200 and ≥ 600 for ZIKV ELISA.

Seroconversion

Seroconversion for ZIKV MN50 titers and ZIKV ELISA titers is defined as ≥ 4 -fold rise from baseline.

Acute Febrile Illness and Acute Rash Illness

Acute febrile illness (AFI) is defined as grade 1 or higher fever on at least 2 consecutive days accompanied by any of the following: new rash not limited to vaccination site, arthralgia, or nonpurulent conjunctivitis. Acute rash illness (ARI) is defined as any new rash not limited to vaccination site.

Laboratory Confirmation of ZIKV or DENV Infection Among Those with AFI or ARI

Among subjects with AFI or ARI, laboratory confirmation of ZIKV or DENV infection will be made by either 1) evidence of acute ZIKV and DENV infection within 14 days of symptom onset (confirmed via PCR) or 2) a 4-fold rise in DENV or ZIKV neutralization titers between samples collected at the last visit prior to and at the first visit following the AFI/ARI illness visit, where available.

Consideration of ZIKV Microneutralization Assay Results in Analysis

The lower limit of quantitation (LLOQ) for ZIKV microneutralization assay results is 10. Any values less than the LLOQ will be assigned a value of 5 by the lab. This imputed value will be used for the purpose of calculating summary statistics such GMT and will be displayed in listings of immunogenicity data. If a subject has a baseline titer below the LLOQ (reported as 5), then they will be considered seroconverted if the post-baseline titer is at least 20 (at least a 4-fold rise). Similarly, a subject with a baseline ZIKV MN50 below the LLOQ will be considered seropositive if the post-baseline titer is at least 10 or 100, as applicable.

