6.4. Covariates and Subgroups

As well as treatment group, subjects will additionally be classified by baseline flavivirus immune status, defined primarily as follows:

- ZIKV Seropositive: any subject with detectable ZIKV antibodies pre-vaccination
- ZIKV Seronegative: any subject without detectable ZIKV antibodies pre-vaccination

Baseline flavivirus immune status will then be further classified into the following groups:

- ZIKV Seropositive and DENV Seropositive
- ZIKV Seropositive and DENV Seronegative
- ZIKV Seronegative and DENV Seropositive
- ZIKV Seronegative and DENV Seronegative

If a subject has inconclusive results for baseline flavivirus immune status, they will not be summarized with either subgroup defined above but will be included in summaries of all subjects pooled.

Subgroups based on baseline flavivirus immune status will be used in analysis of the secondary and exploratory endpoints only. For all tables and figures presenting group-aggregate analyses by subgroup—or any columns, rows, or panels within them—a single stratum must include at least two subjects in order to be generated.

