14.2 Immunogenicity Data

ZIKV Microneutralization Titers

Table 20: ZIKV Microneutralization Antibody (MN50) Geometric Mean Titer (GMT) Results with 95% Confidence Intervals by Time Point, Treatment Group, and Baseline Flavivirus Immune Status – Immunogenicity Population

[Implementation note: If a baseline flavivirus subgroup includes fewer than 2 subjects, the GMT and 95% CI fields will be populated with 'N/A'.]

Time Point	Baseline Flavivirus Immune Status	2.5 mcg ZPIV			5 mcg ZPIV			Placebo		
		n	GMT	95% CI	n	GMT	95% CI	n	GMT	95% CI
Baseline	All Subjects	x	xx	xx.x, xx.x	x	xx	xx.x, xx.x	x	xx	xx.x, xx.x
	Baseline ZIKV Seropositive									
	Baseline ZIKV Seronegative									
	Baseline ZIKV Seropositive and DENV Seropositive									
	Baseline ZIKV Seropositive and DENV Seronegative									
	Baseline ZIKV Seronegative and DENV Seropositive									
	Baseline ZIKV Seronegative and DENV Seronegative									

Repeat Baseline for:

Day 29 (Pre-Dose 2)										
Day 57 (28 Days Post-Dose 2)										
Day 209 (180 Days Post-Dose 2)										
Day 750 (721 Days Post-Dose 2)										
Peak Post-Baseline										

n = Number of subjects in the immunogenicity population with non-missing immunogenicity data at the specified time point.

95% CI = 95% confidence interval based on Student's t-distribution.

Table 21: ZIKV Microneutralization Antibody (MN50) Geometric Mean Titer (GMT) Results with 95% Confidence Intervals by Time Point, Treatment Group, and Baseline Flavivirus Immune Status – Per Protocol Population

Table 22: ZIKV Microneutralization Antibody (MN50) Geometric Mean Fold Rise (GMFR) Results with 95% Confidence Intervals by Time Point, Treatment Group, and Baseline Flavivirus Immune Status – Immunogenicity Population

[Implementation note: baseline results are not included in this table.]

Table 23: ZIKV Microneutralization Antibody (MN50) Geometric Mean Fold Rise (GMFR) Results with 95% Confidence Intervals by Time Point, Treatment Group, and Baseline Flavivirus Immune Status – Per Protocol Population

[Implementation note: baseline results are not included in this table.]

Table 24: ZIKV Microneutralization Antibody (MN50) Seropositivity Results with 95% Confidence Intervals by Time Point, Treatment Group, and Baseline Flavivirus Immune Status – Immunogenicity Population

[Implementation note: If a baseline flavivirus subgroup includes fewer than 2 subjects, the % and 95% CI fields will be populated with 'N/A'.]

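### An MN50 cell in which every titre is below the LLOQ of 10 would print GMT 5 (5.0, 5.0), a zero-width 95% CI, at any sample size from 2 upward

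*SAP*

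**What the plan says.** SAP section 3.3, in the paragraph on microneutralization results, gives the limit and the substitution: "The lower limit of quantitation (LLOQ) for ZIKV microneutralization assay results is 10" and "Any values less than the LLOQ will be assigned a value of 5 by the lab". The 5 is carried into the GMT: "This imputed value will be used for the purpose of calculating summary statistics such GMT". The same paragraph uses it to derive the seroconversion threshold for a subject who starts below the limit.

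SAP section 8.2.1 plans GMT (Tables 20–21) and GMFR (Tables 22–23) with 95% CIs by visit and treatment group, overall and by baseline flavivirus status. The Table 20 shell lists all subjects, the two ZIKV strata and the four joint ZIKV/DENV strata. Its footnote reads: "95% CI = 95% confidence interval based on Student's t-distribution".

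Two rules limit what is printed, and both concern stratum size. SAP section 6.4 says "a single stratum must include at least two subjects in order to be generated". The Table 20 implementation note says "If a baseline flavivirus subgroup includes fewer than 2 subjects, the GMT and 95% CI fields will be populated with" N/A. Neither document mentions a cell with no variation, a censored-data method, or a display for results below the limit.

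**The concern.** A constant that stands in for an unknown value below 10 is treated as a measurement. When every value in a cell is that constant, the t formula returns a width of zero. A reader of Table 20, or of Figures 16–17 where these limits are the error bars, would see the least informative cells shown as the most precise.

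The strata where this could happen matter for the trial's question. SAP section 3.3 says baseline status is determined in order to see whether seropositivity affects response to the vaccine. ZIKV-seronegative subjects at baseline, and placebo recipients throughout, are the reference for reading that response. MN50 GMT by serostatus is a secondary endpoint.

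**Working it through.** **Inputs from the documents.** LLOQ 10 and substituted value 5 (SAP 3.3). Student-t 95% CI (Table 20 footnote). Smallest printed stratum 2 (SAP 6.4 and Table 20 note). Arms of 45 and 5 in Group 1 and 35 and 5 in Group 2 (SAP 4.4.3), so placebo is 5 + 5 = 10, spread over up to four joint strata. Clopper-Pearson limits for titre ≥10 (Table 24 footnote).

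**Assumptions.** The t interval is computed on the log scale, as a GMT implies. Tables 21–23 follow the Table 20 method. The program prints limits when the SD is 0.

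**The plan's own figure.** The one number the SAP derives from the substituted value is the seroconversion threshold: 4 × 5 = 20. It reproduces exactly.

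**Cell wholly below 10.** With y = log10(titre), GMT = 10^ȳ and the limits are 10^(ȳ ± t(0.975, n−1) × s/√n). All y = log10(5) = 0.699, so s = 0 and the half-width is 0 for every n. At n = 2, 3, 5, 10, 35 and 45 the result is GMT 5.0 (5.0, 5.0). If all subjects are below 10 at both visits, each fold rise is 5/5 = 1, so GMFR is 1.0 (1.0, 1.0).

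**What the same cell supports.** With 0 of n titres ≥10, the exact upper limit is 1 − 0.025^(1/n):

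| n | Table 20 | Table 24, share ≥10 (95% CI) |
|---|---|---|
| 2 | 5 (5.0, 5.0) | 0–84.2% |
| 5 | 5 (5.0, 5.0) | 0–52.2% |
| 10 | 5 (5.0, 5.0) | 0–30.8% |

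**How often.** The documents give no share p of titres below 10, so this is a range. The chance that a cell is wholly below is p^n:

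| Assumed p | n = 2 | n = 5 |
|---|---|---|
| 50% | 25% | 3% |
| 80% | 64% | 33% |
| 90% | 81% | 59% |
| 95% | 90% | 77% |

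**One quantifiable titre.** The interval is then no longer degenerate.
- n = 2, titres 5 and 10: ȳ = 0.849, s = 0.213, half-width 12.706 × 0.213/√2 = 1.91. GMT 7.1 (0.09, 578).
- n = 5, one at 10: ȳ = 0.759, s = 0.135, half-width 0.167. GMT 5.7 (3.9, 8.4).
- n = 10, one at 10: GMT 5.4 (4.6, 6.3).
- n = 35, one at 10: GMT 5.1 (4.9, 5.3).

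**The case against.** The strongest reply is that little harm follows. LLOQ/2 substitution is prespecified and conventional. The trial is descriptive, and no test or decision rule uses these intervals. Table 24 gives exact intervals for the share ≥10 in the same cells, and the reverse cumulative distribution curves and Listing 8 show the titres below 10. The SAP introduction describes the population as largely flavivirus-immune, so affected cells may be few. Strata are defined by IgM/IgG assays rather than by MN50, so a ZIKV-seronegative stratum need not be wholly below 10.

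All of that stands as a limit on frequency and consequence. It does not make the printed interval right. Table 24 describes a different quantity and does not change the limits in Tables 20–23 or the bars in Figures 16–17.

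A reader might infer two stronger points.

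- **Mostly censored cells also get near-zero intervals.** The figures above show otherwise. In small cells a single quantifiable titre opens the interval widely. A narrow one needs a large cell with about one value just above 10.
- **The substitution wrecks coverage in general.** With assumed log10-normal titres, true GMT 5 and SD 0.4 (77% below 10), n = 35 gives a mean estimate of 6.6 and coverage of about 6%. But 35 is the size of the whole 2.5 mcg arm, not of a small stratum. At n = 10 the same assumptions give about 86–87%. With about 60% below 10 (true GMT 8, SD 0.4, n = 35) coverage is about 93%. Where the true GMT is well below 5, coverage is poor even in small cells: 0–27% at an assumed true GMT of 2 or 3 with n = 2 to 10. The documents give neither the SD nor the distribution below 10, so they do not show which case applies.

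**Conclusion.** The point holds for cells in which every MN50 titre is below 10. As planned they show no uncertainty at all, at any n from 2 upward, and nothing in the SAP prevents it. The size is a CI of width zero where the companion table allows anything from 0 to 84% (n = 2) or 0 to 52% (n = 5) of titres to be ≥10.

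The degenerate interval follows from the SAP's rules, given the log scale and software that prints limits when the SD is 0. How many cells are affected is unknown. ZIKV-seronegative baseline cells and small placebo cells are the plausible ones.

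The scope is MN50 GMT and GMFR. SAP 3.3 states no limit or substituted value for ELISA. Seropositivity and seroconversion are proportions with Clopper-Pearson limits under section 8.2.1. The documents do not support a general finding against LLOQ/2 substitution.

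**What to change.** In SAP 3.3 and 8.2.1, Tables 20–23 and Figures 16–17:

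1. Where every titre in a cell is below 10, print GMT as '<10' and its CI as 'NE', and draw no error bar.
2. Where all subjects in a cell are below 10 at both visits, print GMFR and its CI as 'NE'.
3. Show n (%) below 10 in each cell, or add a footnote pointing to Table 24 (Table 25 for the per-protocol population).
4. Keep the prespecified value of 5 in all other cells.

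A left-censored log-normal GMT may be added as an optional sensitivity analysis in larger cells with several distinct quantifiable titres. It should not be a mandatory replacement. If the only quantifiable titre is exactly 10, put μ = log10(10) = 1. The likelihood is then proportional to (1/σ) × 0.5^k for k censored values, which grows without bound as σ goes to 0. The fit collapses to GMT 10 with SD 0, another false zero-width answer.

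The cost is a shell note, a footnote and a small programming condition, with no new data. The downside is that some cells will show 'NE'.

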4. INVESTIGATIONAL PLAN

4.1. Overall Study Design and Plan

This study is a single-center, double-blinded, placebo-controlled, Phase 1, dose de-escalation study to evaluate the safety, reactogenicity, and immunogenicity of a purified inactivated, alum-adjuvanted ZIKV vaccine (ZPIV) administered in a homologous prime-boost regimen to healthy male and non-pregnant female adult subjects living in a flavivirus-endemic area. Two dose levels will be evaluated. Each subject will receive either placebo or 5 mcg (Group 1), or 2.5 mcg (Group 2) of ZPIV administered by IM injection. The study will consist of a screening period of up to 28 days, a vaccination period in which subjects will receive a prime dose of vaccine on Day 1 followed by a homologous boost on Day 29, and a follow-up period of 24 months post boost vaccination. See [Table 1](#) of Appendix 1.

As this is a phase I study, the study will begin with enrollment of two sentinel subjects in Group 1 who will receive 5 mcg ZPIV open label. One sentinel subject will be vaccinated, followed for one day for safety and reactogenicity, and if no halting rules are met per determination of the PI and co-PI, then the second sentinel subject will receive 5 mcg ZPIV open-label. Both sentinels will be followed for safety through Day 8 and if no predefined halting rules are met and no safety concerns are identified, then enrollment of the Group 1 non-sentinel subjects will proceed in double-blind fashion. The same procedure will be used for administration of the boost vaccination to the Group 1 sentinels: 1 sentinel will receive 5 mcg ZPIV open-label, be followed for 1 day for safety and reactogenicity, and if no halting rules are met, then the second sentinel will receive the boost vaccine. Both sentinels will be followed until Day 8 after second vaccination for safety and reactogenicity and if no halting rules are then boost vaccination of the non-sentinel Group 1 subjects can proceed. Enrollment of the 2.5 mcg ZPIV group (Group 2) can begin after or at the same time non-sentinel subjects in Group 1 receive the 1st dose of vaccine.

Solicited local and systemic reactogenicity will be recorded through Day 8 after the prime and boost administration of study vaccine by the subject in a memory aid, and will be reviewed with the clinic staff during clinic visits on Days 2 and 8, and during a telephone visit on Day 4. Safety laboratories will be collected on Days 8 and 15 after administration of the prime and boost dose. Unsolicited AEs will be recorded and evaluated by medical history and targeted physical examinations as needed until 28 days after the second vaccination. SAEs, AESIs, and history of new medical conditions with onset after the first vaccination will be collected for the duration of the study.

Blood will be drawn to evaluate humoral immunity to ZIKV and DENV pre- and at multiple visits post-each vaccination, including baseline serology testing on Visit 00 to determine pre-vaccination flavivirus immune status. CPT tubes will be collected and peripheral blood mononuclear (PBMCs) cells will be harvested and stored for future assessment of immunity including cellular and humoral immunity and systems biology.

Subjects who develop an AFI (grade 1 or higher fever on at least 2 consecutive days accompanied by any of the following: new rash not limited to vaccination site, arthralgia, or nonpurulent conjunctivitis) or ARI (new rash not limited to vaccination site) at any time after signing the ICF until the end of study will be asked to contact the clinic within 3 days of symptom onset and return as soon as possible and at least within 14 days for blood and urine collection to evaluate for acute ZIKV and DENV infection. Subjects will also be asked about any history of AFI and ARI at each clinic visit and phone call after Visit 00. Subjects presenting for evaluation of AFI/ARI will have a medical history including travel

history collected, all symptoms recorded, physical exam if indicated, and concomitant medications and AEs collected, regardless of when the visit occurs.

The schedule of study procedures is displayed in [Table 2](#).

4.2. Discussion of Study Design, Including the Choice of Control Groups

The strategy for the initial development of this vaccine is to conduct a series of phase I studies to assess the safety and immunogenicity in flavivirus-naïve and flavivirus-experienced subjects. Because it is not known how previous exposure to flaviviruses will affect the safety and immunogenicity profile of this vaccine, this strategy will address a critical gap necessary to complete an early and rapid assessment of the viability of this ZIKV vaccine candidate. All trials will initiate with a 5 mcg dose. The first two clinical trials will explore the safety and immune response to the vaccine in flavivirus naïve subjects and in subjects that have been previously vaccinated with JEV or YFV vaccines. This trial will be conducted in Puerto Rico, whose population has been exposed to DENV 1-4, ZIKV and potentially YFV and/or WNV. A fourth clinical trial will be conducted by Beth Israel Deaconess Medical Center to evaluate the safety and immunogenicity of an accelerated vaccination schedule with the Zika vaccine candidate in healthy adults. The initial doses and regimens that will be utilized in these initial trials was selected based on experience with other inactivated flavivirus vaccines and recent data from mouse and NHP studies. Experience with licensed flavivirus vaccines suggests a 5 mcg dose should be safe and immunogenic; the 5 mcg dose was safe and protective in a NHP model [1]. Therefore, for these trials, subjects will be enrolled initially in the 5 mcg group. To determine if lower doses of ZPIV are equally or comparably immunogenic to the 5 mcg dose, subjects in this trial will then be enrolled in the 2.5 mcg group, or in a 1.25 mcg group in other trials. ZPIV is intended to be used in flavivirus endemic areas and among US military members and travelers who may have already received another flavivirus vaccine. Therefore, evaluating the safety and immune response in both flavivirus-naïve and flavivirus-immune subjects is important. This study provides the opportunity to evaluate ZPIV among a largely flavivirus-immune population who resides in an area with active ZIKV and DENV transmission.

4.3. Selection of Study Population

Approximately ninety subjects, males and non-pregnant, non-breastfeeding females, 21-49 years of age, inclusive, who are in good health (based on physical examination, medical history and clinical judgment) and meet all eligibility criteria, will be enrolled. The study population's racial and ethnic make-up should reflect the demographics of the larger community at the clinical trial site.

4.3.1. Subject Inclusion Criteria

Subjects eligible to participate in this study must meet all of the following inclusion criteria:

1. Must be a male or non-pregnant, non-breastfeeding female between the age of 21 and 49 years, inclusive at the time of screening and enrollment.
2. Must be willing and able to read, sign and date the informed consent document before study related procedures are performed.
3. Must be willing and able to comply with study requirements and available for follow-up visits for the entire study.
4. Must have a means to be contacted by telephone.

5. Must have a body mass index (BMI) ≥ 18.1 and $< 35.0 \text{ kg/m}^2$.
6. Must have acceptable* screening laboratory findings within 28 days before enrollment.

*Acceptable clinical laboratory parameters include:

- Hemoglobin: women: $\geq 11.5 \text{ g/dL}$; men $\geq 13.5 \text{ g/dL}$
- Hematocrit: women: $\geq 34.5\%$; men $\geq 40.5\%$
- White blood cell count: $\geq 3,500 \text{ cells/mm}^3$ but $\leq 10,800 \text{ cells/mm}^3$
- Platelets: $\geq 150,000$ but $\leq 450,000 \text{ per mm}^3$
- Urine dipstick (clean urine sample): protein $< 1+$, glucose negative
- Serum creatinine $\leq 1 \times$ institutional upper limit of normal (ULN)
- Blood urea nitrogen (BUN) < 25
- Alanine aminotransferase (ALT) and aspartate aminotransferase (AST) $< 1.25 \times$ institutional ULN
- Total bilirubin $< 1.25 \times$ institutional ULN

*Note: If laboratory screening tests are out of acceptable range, repeat of screening tests is permitted once, provided there is an alternative explanation for the out of range value.

7. Must be in good health based on the investigator's clinical judgment when considering findings from past medical history, medication use, vital signs, and an abbreviated physical examination.

Note 1: Good health is defined by the absence of any medical condition described in the exclusion criteria in a subject with a normal abbreviated physical exam and vital signs. If the subject has a preexisting condition not listed in exclusion criteria, it cannot meet any of the following criteria: 1.) first diagnosed in last 3 months; 2.) worsening in terms of clinical outcome in last 6 months; or 3.) involves need for medication that may pose a risk to subject's safety or impede assessment of adverse events or immunogenicity if they participate in study.

Note 2: An abbreviated physical exam differs from a complete exam in that it does not include a genitourinary and rectal exam.

Note 3: Vital signs must be normal by protocol toxicity grading scale or determined to be normal-variant by investigator. In the event of an abnormal heart rate or blood pressure due to physiological variation or activity, the subject may rest for 10 minutes in a quiet room, and then blood pressure and/or heart rate may be re-measured. Repeated vital signs may be used to determine eligibility.

8. Women of childbearing potential* must have a negative serum pregnancy test at screening and a negative urine pregnancy test immediately prior to each vaccination.

Note: All female subjects are considered of childbearing potential unless postmenopausal or surgically sterilized and ≥ 3 months have passed since sterilization procedure. Postmenopausal is defined as amenorrhea for ≥ 12 months without an alternative medical cause. Permanent female sterilization procedures include tubal ligation, bilateral salpingectomy, hysterectomy, bilateral oophorectomy, or successful Essure placement.

9. Women of childbearing potential must use an acceptable method of contraception* from one month (30 days) prior to the first vaccination until the end of the study.

*Acceptable methods of contraception include the following:

-Use highly effective contraceptive methods, defined by <1% failure rate per year independent of user adherence, including long-acting reversible contraception (LARC): progestin-releasing subdermal implants and intrauterine devices (IUD), OR
-Use effective contraceptive methods, defined by 5-9% failure rate with typical use and <1% failure rate with consistent and correct use, including: prescription oral contraceptives, contraceptive injections, combined pill, progestin-only pill, hormone-releasing transdermal patch or vaginal ring, and depot medroxyprogesterone acetate injection (Depo-Provera), OR
-Male sex partners must have had a vasectomy ≥3 months prior to first vaccination, OR
-Practice abstinence defined as refraining from heterosexual intercourse from 30 days before first vaccination until the end of the study.

10. Female subjects must agree to not donate eggs (ova, oocytes) from the start of screening period until the end of the study.
11. Subjects must provide concurrent consent at the time of enrollment and 1st vaccination to future use of stored blood samples to measure immunity to ZIKV.

